# 6. Subject Recruitment

Subjects will be recruited through referring community mental health centers, treatment providers, invited to participate if they are included in our registry, and self-referrals through advertisement and word-of-mouth.

### 7. Study Procedures

The following assessments and procedures will be administered according to the study procedures table (Attachment A). All assessments will be completed by study personnel trained to administer the instruments and will be based on interviews with the subject or questionnaires completed by the subject.

# 8. Clinical Assessments and Procedures

### Primary Efficacy Outcome Measures:

Negative Symptom Assessment Scale – 16-item (NSA-16), a primary outcome measure, is used to help clinicians rate behaviors (not psychopathology) commonly associated with negative symptoms of schizophrenia. The scale rates subjects on 16 "anchors," is a semi-structured, clinical interview, and each item is rated from 1 to 6. The total score is the sum of the 16 specific items and ranges from 16 to 96; a higher score indicates greater severity of illness. In addition, there is a global rating which represents the overall assessment of a subject's negative symptoms. The rating should not be an average of any particular behavior, but a gestalt of everything observed in the interview (58).

Hopkins Verbal Learning Test-Revised, Wechsler Memory Scale-Third Ed, Spatial Span, and Letter-Number Sequencing are cognitive tests for verbal memory (Hopkins) and working memory (Spatial Span and Letter-Number Sequencing combined as a single composite score). These tests are part of the MCCB (48) which has proven reliability for clinical trials of cognitive impairment associated with schizophrenia. For each cognitive test, a multi-item score will be derived based on the raw item values according to the MCCB scoring manual. Each of the individual item raw scores is standardized to ageand gender-corrected t-scores (mean=50, standard deviation=10). Each working memory test will be converted in to a single domain score.

#### Secondary Outcome Measures:

**MATRICS Consensus Cognitive Battery (MCCB)** will be administered in its entirety at baseline, Visit 4, and the end of study. It is a reliable cognitive battery (test-retest reliability ~0.7 for most tests, (48). Small but statistically significant practice effects have been noted with speed of processing and problemsolving subtests (1/5th of standard deviation). To overcome these practice effects, alternate forms of MCCB will be implemented in this study. The total average administration time of MCCB is approximately 75 minutes. MCCB is comprised of seven cognitive domains and 10 related tests (Trail Making Test: Part A; Brief Assessment in Cognition in Schizophrenia: Symbol Coding; Hopkins Verbal Learning Test-Revised; Wechsler Memory Scale-Third Ed: Spatial Span; Letter-Number Sequencing; Neuropsychological Assessment Battery: Mazes; Brief Visuospatial Memory Test-Revised; Category Fluency: Animal Naming; Mayer-Salovey-Caruso Emotional Intelligence Test: Managing Emotions; and Continuous Performance Test-Identical Pairs). For each cognitive test, a multi-item score will be derived based on the raw item values according to the MCCB scoring manual. Each of the individual item raw scores is standardized to age- and gender-corrected t-scores (mean=50, standard deviation=10). Each test

Version: 05.01.17 (Amendment L) Page 17 of 36 will be converted in to a domain score, with Working Memory and Speed of Processing domains consisting of 2 and 3 tests, respectively.

Note: At day 14 and 42 only the Hopkins Verbal Learning Test-Revised, Wechsler Memory Scale-Third Ed: Spatial Span, and Letter-Number Sequencing will be administered. At day 0, 28, and 56, the entire MCCB will be administered and the 3 tests that constitute primary outcome measures will be administered prior to the administration of the remainder of the MCCB so test administration order is maintained throughout the trial for the cognitive primary outcome measures.

Clinical Global Impression Severity Scale (CGI-S) (59) will be used for repeated evaluations of global psychopathology. The CGI-S scale is widely used in schizophrenia research and is a single 7-point Likert scale rating severity of psychopathology on a scale of 1 (normal, not ill) to 7 (very severely ill).

Clinical Global Impression Change Scale (CGI-I) (59) is used to assess the clinical change as compared to symptoms at baseline using a 7-point Likert scale, ranging from very much improved (1) to very much worse (7).

The Positive and Negative Syndrome Scale (PANSS) (60) is an assessment instrument for general psychopathology and positive symptoms. The PANSS contains 30 items that assess symptoms of psychotic disorders including positive, negative and general psychopathology. The PANSS was chosen because of its widespread use in clinical studies of psychosis, and its demonstrated reliability in assessing psychopathology across diverse patient populations.

Personal and Social Performance Scale (PSP) (61) is a 100-point, single item, clinician rated scale to assess 4 domains of functioning, including personal and social relationships, socially useful activities, self-care and disturbing and aggressive behaviors.

**Quality of Life Scale (QLS)** (62) assesses multiple dimensions of quality of life. It was developed specifically for schizophrenia populations and is commonly employed in clinical trials.

**Barnes Akathisia Scale (BARS)** (63) is used to rate drug-induced akathisia. Symptoms are rated on a 4-point scale, with 0 being no akathisia and 3 being severe akathisia. A global clinical assessment of akathisia is then scored on a 6-point scale, with 0 being no evidence of akathisia and 5 being severe akathisia.

Simpson Angus Scale (SAS) (57) is a 10-item scale used to evaluate the presence and severity of drug induced Parkinsonism. Each item is rated from 0 to 4.

Calgary Depression Scale for Schizophrenia (CDSS) (64) is a nine-itemed structured interview specifically developed for assessment of depression in patients with schizophrenia. Items are scored from 0 (absent) to 3 (severe).

Columbia Suicide Severity Rating Scale (C-SSRS) (65) captures the occurrence, severity, and frequency of suicide-related thoughts and behaviors during the assessment period. The definition of behavioral suicidal events used in this scale is based on those used in the Columbia Suicide History Form (66). During the baseline assessment, questions are in relation to lifetime experiences and all subsequent questioning is in relation to the last assessment.

Anticholinergic Cognitive Burden Scale (ABS) (56) was developed by an interdisciplinary group of pharmacy and medical professionals using a systematic review identifying drugs with anticholinergic activity established in the literature. Drugs are categorized based on their clinically relevant cognitive

Version: 05.01.17 (Amendment L) Page 18 of 36 effects. Summed scores reflect the total clinically relevant anticholinergic effects on cognition of all medications in a subject's drug regimen, with higher scores denoting higher burden.

#### MRI Methods

MRIs will be performed at the IU Center for Neuroimaging using an integrated 90-minute exam including structural and functional MRI (fMRI). All scans will be completed on a newly installed (June 2012) research-dedicated Siemens MAGNETOM Skyra 3T 70cm bore whole body scanner using a 32-channel head coil. Scans will include structural series for registration with functional tasks, to examine white matter integrity, and to rule out incidental findings, and fMRI and MR perfusion measures. FMRI tasks will focus on episodic and working memory. Positioning and motion: Subjects are instructed to Figure 2. N-Back Task

remain still during scanning and deformable foam cushioning is used to stabilize the head. Real time image reconstruction and processing are used for quality assurance at the time of scanning. If there is any problem the scan is repeated. For fMRI, minor subvoxel-level translation or rotation is adjusted during post-processing. Noise: Noise-attenuating headphones and ear stopples provide excellent noise reduction and permit adequate auditory perception. **Longitudinal repositioning**: We will employ Siemens AutoAlign scanner software to help ensure maximum reproducibility. AutoAlign, which uses a 3D atlas for automated slice positioning, appears robust and to yield repeatable and accurate repositioning (67). **Structural Imaging Sequences** include: (1) Sagittal survey 3-plane localizer (2) Sagittal T1-weighted MP-RAGE 3D anatomical volume (3) 3D fluid attenuated inversion recovery (FLAIR) and (4) Diffusion tensor imaging (DTI). **Functional MRI Sequences** include: Echo-planar functional MRI and GRE Field map.

fMRI activation tasks: fMRI activation tasks will include Visual-Verbal 2-Back, Scene Encoding and Recognition, and Resting Connectivity paradigms, shown by our group and others to demonstrate reliable activation for the cognitive functions and brain regions of interest (68-78). We have successfully implemented all tasks in multiple studies of patients with psychosis and other clinical populations, as well as in pharmacological imaging studies, and have detected task-related activation in expected brain regions.

2-Back Visual-Verbal working memory task: Verbal working memory has been widely studied in terms of cognitive components and models (79-83), neural circuitry of the frontal lobes and basal ganglia (84), and its disruption in brain disorders such as schizophrenia (45, 85), MS (78, 86), and MTBI (70, 71), as well as in relation to estrogen status (11, 12, 87, 88). Subjects view a string of consonant letters (except L, W, and Y). The working memory load is varied parametrically via three task conditions: 0-back, 1-back, and 2-back (Figure 2). The 0-back control condition has a minimal working memory load; subjects are asked to decide if the current letter matches a single target letter that is specified before the epoch begins. In the 1-back condition, they are asked to decide if the current letter matches the previous one. During the 2-back condition, the task is to decide whether the letter currently presented matches the letter that has been presented two back in the sequence. In our previous studies, this task has been highly robust in producing bilateral

frontal and parietal activation in healthy young and elderly controls and sensitive to differences in patient groups (70, 71, 77, 78). Task length 6:09.

Version: 05.01.17 (Amendment L) Page 19 of 36

Scene Encoding and Recognition tasks: These tasks utilize stimuli and a task design modified from that used by Detre et al. in episodic memory studies in temporal lobe epilepsy (68, 69, 74). In their published studies and Drs. [name] and [name]' initial work, these tasks elicit reliable bilateral MTL activation in healthy children, adolescents, and adults, with a slight right hemisphere predominance. During the blocked-design encoding trial subjects attempt to encode complex scenes for later recognition (Figure 3).

The control condition consists of repetition of a single degraded version of one of the encoding stimuli. During the event-related recognition trial the subject views target scenes intermixed with foils, and is asked to decide which were presented during the encoding trial. Task length for each trial is 5:15.

Pseudo-Continuous Arterial Spin Labeling (pCASL) perfusion images will also be acquired to quantify any drug related changes in cerebral blood flow. Subjects are asked to lie still and keep their eyes closed. Task length 5:14.

Functional Imaging Stimulation and Physiological Monitoring Procedures: All stimuli are presented through an MR-safe and compatible headphone and projector system (Psychology Software Tools, Inc.). Experimental tasks are presented by PC interface and are programmed using the Presentation software package. Responses are recorded electronically through an MRI compatible fiber optic button response system (Current Designs, Inc.). This custom device is also connected to the sync pulse output of the scanner's gradient amplifier and sends a TTL signal to the PC marking the time each volume is acquired for synchronization between scans, event-related fMRI stimuli, and button responses. A comprehensive physiological monitoring system will be used with synchronized digital recording including pulse oximeter, respiratory belt, HR and BP measures, which will be available for analysis in relation to BOLD fMRI and PASL time series.

### Event Related Potentials (ERP) Methods

Electroencephalography (EEG) will be recorded from a 32 channel, silver/silver-chloride scalp electrode montage using Neuroscan Inc. SYNAMPS-2 bioamplifier with a bandpass of .1 to 200 Hz (24 dB/octave roll off). Electrode impedance will be maintained below 5 kOhms. EEG will be recorded continuously during the stimulus paradigms. Three minute periods of resting EEG will be recorded for eves open and eyes closed prior to the ERP paradigms. All three ERP measures are highly sensitive to schizophrenia, with an effect sizes (d) > 0.7 (7, 89). Auditory Steady State Response (ASSR) which synchronizes to the frequency and phase of periodic auditory stimuli, will be used to test auditory pathway integrity and possible ER $\beta$  modulation of glutamate and GABA transmission (90, 91). ASSR power in the gamma range (40 to 59 Hz) is usually reduced in schizophrenia (d > .8; 10). Gamma frequency entrainment will be obtained to a series of 100 click trains (40 Hz; 1000 ms duration; 500 ms ISI; 90 dB). After digital filtering (.1 to 55 Hz), ocular correction and artifact rejection, averaging (100 ms baseline and 1000 ms post-stimulus epoch) and baseline correction, we will measure event-related spectral perturbation (ERSP; mean power relative to baseline) at Fz to 40 click train stimulation (92), and predict larger ERSP values in treated patients. Phase locking factor (inter-trial coherence) will also be measured, since this measure of synchrony is often affected in schizophrenia as well (7). In addition, we will obtain QEEG recordings during the same ERP/MMN testing sessions. This measure is one of the most commonly used indices to confirm CNS penetrance and cortical activity in early stage CNS drug development. Increased average alpha power (8 to 13 Hz) across the set of electrode sites determined by QEEG in LY500307 treated subjects compared to placebo treated subjects will be the measure of activity utilized in this study. Mismatch Negativity (MMN) is an ERP component elicited by a deviant tone interpolated in a series of standard tones which indexes pre-attentive sensory memory, and is generated by the auditory and frontal cortices (89). MMN amplitude is reduced in schizophrenia and has been correlated with level of psychosocial function in schizophrenia and degree of grey matter loss in frontal cortex and Heschl's gyrus

Version: 05.01.17 (Amendment L) Page 20 of 36 (93). MMN will be recorded to infrequent 1.2 kHz tones (0.05 probability, 50 ms duration) amid frequent 1.0 kHz tones, with a 300 ms ISI and total of 1,600 tone presentations. After digital filtering (.01 to 24 Hz), ocular correction and artifact rejection, averaging by condition (100 ms baseline and 300 ms poststimulus epoch) and baseline correction, the standard ERP will be subtracted from the deviant ERP. MMN will be measured as the most negative sample in the difference waveform between 100 and 300 ms period at Fz, and it is predicted that MMN will be increased in treated subjects. Auditory P300 component indexes working memory during stimulus discrimination and is decreased in schizophrenia with an effect size of about 0.9 (89). ERPs will be elicited by infrequent target tone-pips of 40-ms duration presented pseudo-randomly, interspersed among frequent low-pitched tones (1000 Hz, 90 dB) with 1 s ISIs and 600 trials. Subjects will respond to infrequent target tones using a button press. Target ERP trials will be processed off line, using digital filtering with a low pass of 24 Hz, ocular correction, and artifact rejection for trials with data points exceeding  $\pm$  100 microvolts prior to averaging trials within each condition. After averaging using the epoch -100 to 600 ms after stimulus onset, P300 latency will be measured at the largest positive voltage sample between 280 and 600 ms at the Pz electrode site of the target ERP relative to baseline. Peak amplitude will be measured as the mean voltage between + 20 ms about the peak latency at the Pz electrode site. It is predicted that P300 peak voltage will be greater, and P300 latency shorter in treated subjects. Total ERP testing time: about one hour.

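### The P300 amplitude window can run 20 ms past its epoch, and the ASSR power reference, as written, rests on a 100 ms baseline beside onset with no time-frequency window stated

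*Combined protocol and SAP*

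**What the plan says.** All processing rules are in Section 8, Event Related Potentials (ERP) Methods. EEG is recorded continuously during the paradigms.

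- **P300.** Tones come "with 1 s ISIs and 600 trials". The epoch and latency rule begins "After averaging using the epoch -100 to 600 ms after stimulus onset, P300 latency will be measured at the largest positive voltage sample". The sample sought is the "largest positive voltage sample between 280 and 600 ms at the Pz electrode site", and the amplitude rule is "Peak amplitude will be measured as the mean voltage between + 20 ms about the peak latency at the Pz electrode site".
- **ASSR.** One hundred 40 Hz click trains are given, each lasting 1000 ms, with a 500 ms interval. After filtering and artifact rejection the order is "averaging (100 ms baseline and 1000 ms post-stimulus epoch) and baseline correction, we will measure event-related spectral perturbation", which the plan defines as mean power relative to baseline, at Fz. No wavelet or window length is given. Phase locking, described as inter-trial coherence, is also to be measured.

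Section 3 (Primary Aim 1) lists both paradigms among the secondary measures of target engagement. Section 16 (Event Related Potentials Analyses) predicts larger P300 amplitude, shorter P300 latency and greater ASSR power on LY500307.

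**The concern.** For the P300, the search may legitimately return a peak so close to the end of the epoch that the amplitude rule has no data to work on. The plan does not say what to do then, or what to do when the largest sample is simply the last one searched. Two analysts could score the same recording differently.

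For the ASSR, the outcome is a ratio, so noise or signal in the denominator passes straight into the result. A 100 ms stretch holds few cycles of the frequency measured. It also adjoins stimulus onset, so a longer analysis window would draw post-stimulus signal into the reference and compress the ratio. Computing power after averaging would make the ratio more sensitive to such leakage, because averaging raises the signal-to-noise ratio.

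At stake is the reproducibility and precision of two secondary markers of target engagement.

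**Working it through.** The plan states no numerical result on this point to reproduce. The check is interval arithmetic on its windows, followed by a leakage calculation under stated assumptions.

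**P300** (inputs: epoch end 600 ms, search 280 to 600 ms, half-width 20 ms)

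Latest point needed: 600 + 20 = 620 ms. Overrun: 620 - 600 = 20 ms. First affected latency: 600 - 20 = 580 ms. Affected share of the search range: 20/320 = 6.25%. This is a share of the range, not of subjects, because no latency distribution is given.

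| Peak (ms) | Missing from the 40 ms window |
|---|---|
| up to 580 | 0 ms |
| 590 | 10 ms |
| 600 | 20 ms (half) |

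The sign is printed as a plus. I read it as plus or minus; the upper limit is 620 ms on either reading.

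Effect on amplitude, assuming a cosine-shaped peak of 300 ms period: 20 ms is 0.4189 rad and 10 ms is 0.2094 rad. The full-window mean is sin(0.4189)/0.4189 = 0.971. For a peak at 590 ms the truncated mean is (0.4067 + 0.2079)/(0.4189 + 0.2094) = 0.978, a difference of +0.7%. At 600 ms the remaining half gives 0.971 again, a difference of 0%.

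**ASSR: position of the baseline**

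A 1000 ms train with a 500 ms interval means the interval runs from offset to onset. The 100 ms baseline therefore lies 400 to 500 ms after the previous train. One 40 Hz cycle is 25 ms, so 100 ms holds 4 cycles.

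| Analysis window | Fits wholly in -100 to 0 ms? |
|---|---|
| 3 cycles (75 ms) | yes, centres -62.5 to -37.5 ms |
| 4 cycles (100 ms) | at one centre only, -50 ms |
| 5 or more cycles (125 ms or longer) | no |

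From 200 ms upward, no window that fits within the -100 to 1000 ms epoch is centred before onset.

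**ASSR: size of any leak** (assumes Gaussian wavelets; the response starts at full strength after delay d)

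Leak L = mean over -100 to 0 ms of Φ((t - d)/σ)², with σ = cycles/(2π × 40 Hz).

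| Delay d | 3 cycles | 7 cycles | 10 cycles |
|---|---|---|---|
| 0 ms | 1.4% | 3.3% | 4.6% |
| 20 ms | 0.006% | 0.5% | 1.4% |
| 30 ms | about 0% | 0.15% | 0.65% |
| 50 ms | about 0% | 0.008% | 0.11% |

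Measured ERSP = 10·log10((S + 1)/(L·S + 1)), where S is the 40 Hz signal-to-noise ratio. For a true 50% rise in response power with no leak, S = 10 gives 10·log10(16/11) = 1.63 dB and S = 100 gives 10·log10(151/101) = 1.75 dB. With leakage, the same rise appears as follows.

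| S | Delay | 3 cycles | 7 cycles | 10 cycles |
|---|---|---|---|---|
| 10 | 0 ms | 1.37 dB | 1.12 dB | 0.99 dB |
| 10 | 30 ms | 1.63 dB | 1.60 dB | 1.50 dB |
| 100 | 0 ms | 0.64 dB | 0.34 dB | 0.25 dB |
| 100 | 30 ms | 1.75 dB | 1.47 dB | 0.97 dB |

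On single trials with S = 1, the loss is 3 to 10% at zero delay and about 1.5% or less at 30 ms. With a -400 to -100 ms baseline the leak is under 0.0001% for 3, 7 and 10 cycles, even at zero delay.

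**ASSR: precision**

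If baseline samples were independent, going from 100 to 300 ms would cut the baseline-driven SD by 1 - √(100/300) = 42%. Smoothing makes neighbouring samples overlap. In a simulation with assumed noise and 3- or 7-cycle wavelets, the cut was about 30 to 40%.

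**The case against.** The strongest case is that only a 20 ms boundary slip is proven. Four of its arguments deserve an answer.

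- **The ASSR baseline is not shown to be contaminated.** This stands. A reader might infer that the response certainly leaks into the baseline and could reduce a 1.75 dB effect to 0.25 dB. That needs a zero-latency response, ten-cycle wavelets, a signal-to-noise ratio of 100 and averaging first, all together. The documents support only the last, through word order. Section 16 refers the ERP analysis to earlier protocols, which may fix the window. The 100 ms may also be only the voltage baseline, since the plan does not restate which interval serves as the power reference.
- **Phase locking implies single trials.** This stands too. A reader might infer that the plan takes phase locking from an average, which is impossible. Calling it inter-trial coherence already implies that single trials are kept. What is missing is a statement that ERSP uses them as well.
- **The ASSR epoch is not too short for the response.** This is correct: the 1000 ms post-stimulus epoch covers the whole train. The weakness is in the baseline only.
- **The P300 latency cap is not an epoch error.** This is also correct. The 600 ms ceiling comes from the chosen search window, and a longer epoch alone would not move it. Nor is it shown that truncation shrinks an amplitude effect, since for a symmetric peak the change is under 1%.

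None of this makes the amplitude rule computable after 580 ms, supplies the missing time-frequency window, or makes four cycles a precise reference.

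**Conclusion.** The point holds in a limited form and is a low-priority improvement.

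For the P300, the stated rules are inconsistent for peaks from 580 to 600 ms, where up to half of the amplitude window is outside the epoch. The numerical consequence is small if the waveform is smooth and roughly symmetric about its peak. A waveform still rising at 600 ms is a different case and is not covered by that estimate. How many subjects are affected cannot be known from the documents.

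For the ASSR, the plan as written uses a short reference beside onset and leaves the analysis window open. Loss of precision is the firmer part, subject to the simulation's noise and wavelet assumptions and to the 100 ms being the power baseline. Bias from leakage is conditional: it arises if windows exceed about 100 ms, and it ranges from near zero to material depending on wavelet length and response latency. The documents do not support a claim that these choices will mask a drug effect.

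No primary endpoint, alpha or power figure depends on either part.

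**What to change.** 1. **P300.** Cut the epoch from the continuous EEG to at least 620 ms and keep the 280 to 600 ms search. Tones are 1 s apart, so there is room. Flag any maximum that falls on the edge of the search window, and state how flagged records are scored.
2. **ASSR.** State that ERSP and phase locking are computed on single trials, and give the time-frequency method and window length. Take the power baseline from the 500 ms silent interval, for example -400 to -100 ms. This leaves 100 ms clear of each train, so a window of up to 200 ms (8 cycles) touches neither.
3. **Timing.** Fix these rules before unblinding and apply them identically to Stage 1 and Stage 2 recordings, which are pooled in the final analysis.

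The cost is reprocessing stored recordings and a short amendment to the ERP methods text. No subject needs to be retested.
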